5.6.4 ANTI-DRUG (BAN2401) ANTIBODIES (ADA)

Definitions for BAN2401 Treatment Arms

ADA analysis for BAN2401 treatment arms will be based on evaluable subjects, which is defined as subjects who were treated with BAN2401 and had at least one valid post treatment ADA sample. ADA positive subjects are defined as those subjects with a treatment-induced or treatment-boosted ADA response, where treatment-induced response means ADA developed following drug administration, and treatment-boosted response means ADA already existed before treatment and boosted to a higher titer following drug administration. ADA negative subjects are those without a treatment-induced or treatment-boosted ADA response. It is possible in some instances that some subjects who did not have a measured positive ADA response during the treatment period (i.e., were negative for ADA) may not be confirmed negative due to drug interference in the sample testing process. Those subjects will be classified as ADA negative*. This distinction will be reserved only for those subjects who had PK level \geq drug tolerance limit of the assay and did not have positive ADA samples at any visits, and did not have ADA samples collected at the 3-month follow up visit. If a subject had a negative sample at the 3-month follow up visit and negative samples at all previous visits, then the subject is considered to be confirmed ADA negative. ADA incidence rate is defined as the proportion of ADA positive subjects among all ADA evaluable subjects.

Definitions for Placebo Treatment Arm

For placebo arm, subjects are unevaluable for an immune response to study drug treatment but will be evaluated for a baseline ADA response. Placebo subjects with a baseline ADA response are defined as those with at least one positive ADA sample at any visit.

ADA prevalence rate is defined as the proportion of subjects with baseline ADA response in placebo arm plus BAN2401 subjects with positive ADA samples prior to treatment among all treated subjects.

Analysis

ADA incidence rate and the maximum titer for ADA positive subjects will be summarized by treatment group. ADA prevalence rate will also be summarized.

Clinical efficacy data will be analyzed by ADA subgroups (positive/negative). Analyses will also be performed to investigate the potential association between ADA and AEs that can be attributed to immunogenicity. For the efficacy and safety analyses, ADA negative and ADA negative* subjects will be combined into one negative group.

The efficacy and safety analyses will also be repeated for neutralizing ADAs.

More analyses for ADA/neutralizing ADA will be described in a separate ADA analysis plan document. The correlation between ADA and PK profile will also be evaluated. Details of such analyses will be described in the PK/PD analysis plan.

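### The ADA prevalence rate adds placebo subjects positive at any visit to BAN2401 subjects positive only before treatment, contrary to the SAP's own definition of baseline

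*SAP*

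**What the plan says.** Section 5.6.4 sets separate ADA definitions for the BAN2401 arms and for placebo.

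- **Placebo.** "For placebo arm, subjects are unevaluable for an immune response to study drug treatment but will be evaluated for a baseline ADA response". The baseline response is then defined by samples from the whole study: "Placebo subjects with a baseline ADA response are defined as those with at least one positive ADA sample at any visit".
- **Prevalence.** One pooled rate counts the placebo responders so defined, "plus BAN2401 subjects with positive ADA samples prior to treatment among all treated subjects".
- **Incidence.** "ADA incidence rate is defined as the proportion of ADA positive subjects among all ADA evaluable subjects". The evaluable set is "subjects who were treated with BAN2401 and had at least one valid post treatment ADA sample", so placebo has no incidence rate.
- **Output.** "ADA incidence rate and the maximum titer for ADA positive subjects will be summarized by treatment group. ADA prevalence rate will also be summarized".

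Three other places bear on this. Section 8 defines the baseline value for efficacy and safety as the latest one reported before first dosing, and Section 8.1 likewise uses the last assessment on or before the first-dose date. Section 5.6 lists anti-BAN2401 antibody titers among the safety evaluations, so that definition covers ADA. The end of Section 5.6.4 leaves further ADA analyses to a separate plan that is not shown.

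**The concern.** A rate described as baseline ADA should count the same thing in every arm. Here a BAN2401 subject can be counted only on pre-treatment samples, while a placebo subject can be counted on any sample during the study. The same sequence, negative before dosing and positive later, is a treatment-induced response on BAN2401 and a baseline response on placebo.

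What is at stake is the meaning of one descriptive rate. A reader of the clinical study report would take it as the share of subjects with pre-existing antibody. As defined, it also depends on how often placebo subjects are sampled and on how large the placebo arm becomes under response-adaptive randomization. Neither has to do with pre-existing antibody.

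**Working it through.** The SAP gives no ADA rate, so there is no figure to reproduce. The check is one of logic, followed by an illustration.

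**1. Direction.** Keep the denominator at all treated subjects. Every placebo subject with a positive pre-treatment sample also has a positive sample at some visit. The placebo count under the SAP rule is therefore at least the pre-treatment count, and the BAN2401 count is the same under both rules. The pooled rate can only be equal or higher.

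**2. Conflict with Section 8.** Take a placebo subject who is negative before the first infusion and positive only at a later visit. Under Section 8 the baseline is negative. Under Section 5.6.4 the subject has a baseline ADA response. Both statements cannot stand.

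**3. Illustration.** Inputs:

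- *s*, placebo share: 179.1/683.1 = 26.2% (simulation plan, Table 9.2, null scenario). For comparison, 56/196 = 28.6% in the burn-in (simulation plan, Section 4.0), and 137.6/535.9 = 25.7% is the lowest in Table 9.2.
- *p*, true pre-treatment positivity: assumed 5% (range 2 to 10%).
- *f*, chance that a placebo subject negative before treatment tests positive at one post-dose sample: assumed 0 to 1% (wider range 0 to 2%).
- *k*, number of post-dose samples: assumed 6 (range 3 to 9).

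Samples are treated as independent. Then

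- placebo any-visit rate = p + (1 − p) × [1 − (1 − f)^k]
- pooled rate = p + s × (1 − p) × [1 − (1 − f)^k]
- consistent pre-treatment rate = p

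With p = 5%, f = 1%, k = 6: 1 − 0.99^6 = 0.0585; 0.95 × 0.0585 = 0.0556; placebo rate = 10.6%; excess = 0.262 × 0.0556 = 0.0146; pooled rate = 6.5%.

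| p | f | k | Placebo any-visit | Pooled (s = 26.2%) | Ratio to p |
|---|---|---|---|---|---|
| 5% | 0 | any | 5.0% | 5.0% | 1.00 |
| 5% | 0.5% | 6 | 7.8% | 5.7% | 1.15 |
| 5% | 1% | 3 | 7.8% | 5.7% | 1.15 |
| 5% | 1% | 6 | 10.6% | 6.5% | 1.29 |
| 5% | 1% | 9 | 13.2% | 7.2% | 1.43 |
| 5% | 2% | 9 | 20.8% | 9.1% | 1.83 |

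The three rows with f = 1% show the dependence on sampling: the true rate stays at 5%, while the reported rate moves from 5.7% to 7.2%. With f = 1% and k = 6, raising the placebo share to 28.6% moves 6.5% to 6.6%. Over the full ranges of s, p, f and k the ratio runs from 1.00 to 3.33 and is never below 1. The top value needs p = 2%, f = 2%, k = 9 and s = 28.6% together.

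**The case against.** The placebo rule has a reason. Placebo subjects never receive BAN2401, so they cannot mount a response to it, and any positive sample can be read as reactivity unrelated to drug. Calling them unevaluable for a treatment response is defensible on that ground. But this argument supports reporting any-visit placebo positivity as a background rate. It does not support naming it baseline or adding it to a pre-treatment count.

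The size is also open. Persistent reactors would mostly be positive before treatment already and would add little. Correlation between a subject's samples would shrink the excess below the independence figures. If no initially negative placebo subject ever turns positive, there is no excess. All of this stands.

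Three stronger readings are tempting, and the document does not support them:

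- *That the plan discards the background rate or leaves it invisible.* Placebo samples are evaluated at all visits, and the any-visit rate is a crude background measure. What this SAP does not list is a placebo rate on the induced-or-boosted definition used for incidence. The separate ADA analysis plan may contain one.
- *That a placebo rate could be subtracted from BAN2401 incidence.* Section 5.6.4 itself says that drug in the sample can leave a negative result unconfirmed. Drug-free and drug-containing samples are not equivalent.
- *That the rule weakens the planned analysis of ADA against adverse events, and that a new definition would repair it.* The placebo rule does not touch the positive or negative label of any BAN2401 subject. Neither does the fix.

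**Conclusion.** The point holds as an inconsistency in the definition of ADA prevalence. Section 5.6.4 mixes two ascertainment rules in one numerator and conflicts with the baseline definition in Section 8. That the bias is upward or nil follows from the definitions and needs no assumption. Its size cannot be found from the SAP: 5.0% to 6.5% against a true 5.0% is an illustration that rests on assumed positivity rates, an assumed six post-dose samples and independence between samples.

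The consequence is limited to one descriptive immunogenicity rate and how it is read. BAN2401 incidence, maximum titer, the ADA subgroups of BAN2401 subjects, the primary analysis, the sample size and the error rate are untouched. It should be corrected because the text contradicts itself and the correction is cheap.

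**What to change.** 1. In Section 5.6.4, define baseline ADA in every arm, placebo included, from samples taken before the first dose, in line with Section 8, and compute prevalence from that definition only.
2. Report placebo post-dose positivity separately. Apply the newly-positive or boosted-titer definition to placebo and show it as a descriptive background column beside the BAN2401 incidence. Add a note that drug interference in active-arm samples rules out simple subtraction. If the separate ADA analysis plan already has this table, a cross-reference is enough.

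The cost is a few sentences of SAP text and at most one table column. The any-visit rule already implies that post-dose placebo samples are tested, so no new assay work should be needed.

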5.3.4 Examination of Subgroups

The primary endpoint, key secondary endpoints, secondary endpoints and exploratory endpoints related to clinical assessments and biomarkers will be analyzed using the mixed-effects model with repeated measures to evaluate the following subgroups; age ≤ 65 , $65 < \text{age} < 80$, age ≥ 80 , gender, ethnicity, race, region, clinical subgroup (MCI due to AD, Mild Alzheimer's Disease Dementia), *APOE ε4 carrier status* (positive (overall, heterozygous and homozygous) or negative), and the presence or absence of ongoing AD treatment (i.e., AChEIs and/or memantine), subjects with/without neutralizing ADA, and biomarker subgroups defined in [Section 5.8](#).

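### ADA status is set by a response at any time after dosing and then used as a fixed positive/negative split, with no time-order or exposure rule, so an ADA-AE comparison can mislead in either direction

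*SAP*

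**What the plan says.** Section 5.6.4 makes a BAN2401 subject evaluable if the subject was treated and "had at least one valid post treatment ADA sample". Then "ADA positive subjects are defined as those subjects with a treatment-induced or treatment-boosted ADA response", where "treatment-induced response means ADA developed following drug administration" and a boosted response is a rise in the titer of pre-existing ADA. No visit or time limit is attached to either. A negative is confirmed only if the 3-month follow-up sample and all earlier samples are negative. A further category covers negatives that drug interference may have masked. Those subjects had drug levels at or above the assay's tolerance limit, "did not have positive ADA samples at any visits", and had no follow-up sample.

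The same section analyzes clinical efficacy by ADA positive and negative subgroups and announces the ADA-AE association analysis: "Analyses will also be performed to investigate the potential association between ADA and AEs that can be attributed to immunogenicity". It then merges the two kinds of negative: "For the efficacy and safety analyses, ADA negative and ADA negative* subjects will be combined into one negative group". Efficacy and safety are repeated for neutralizing ADA. Further ADA analyses are left to a separate plan.

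Section 5.3.4 lists "subjects with/without neutralizing ADA" among the MMRM subgroups, beside age, gender and region. Section 5.6.2 counts TEAEs up to 90 days after the last dose and does not refer to ADA timing.

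**The concern.** ADA status under this definition is learned during follow-up. A subject who stays longer gives more samples and has more time both to become positive and to have an AE. A subject who leaves early has less of each. Sorting subjects by status at the end of follow-up and comparing AE frequencies mixes any effect of ADA with time on drug, and it attributes to ADA events that came before ADA was detected.

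The opposite error is also possible, and it matters more for safety. If an AE ends dosing and sampling before ADA is detected, the subject stays in the negative group. An immunogenicity signal could then be hidden or even look protective.

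For efficacy, the split conditions on a post-baseline variable. Section 5.6.4 declares placebo subjects unevaluable for an immune response to study drug, so an ADA-positive or ADA-negative active subgroup has no matching placebo group.

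**Working it through.** The SAP gives no ADA rate, AE rate or power for this analysis, so there is no stated figure to reproduce. The check is a simulation with **no true ADA-AE link**.

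**Inputs from the SAP**
- Treatment lasts 18 months (Section 6.3).
- Dropout is exponential, 20–40% by 12 months (Section 4; Appendix 13.2, Section 6.0). Input check: 40% at 52 weeks implies 1 − 0.6^0.5 = 22.5% at 26 weeks, against the stated 22%.
- Only subjects with at least one post-dose sample are analyzed (Section 5.6.4).

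**Assumptions, not in the SAP**
- Sampling every 3 months while on drug.
- Seroconversion 20–40% and AE risk 10–30% by 12 months, at constant hazard.
- Study dropout stands for the end of both dosing and sampling.
- In the early-onset variant, ADA arises at a mean of 2 months.

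**Method.** Each monthly hazard is −ln(1 − p)/12. For dropout this gives 0.0186 at 20% and 0.0426 at 40%. A subject is positive if the first sampling time at or after onset falls before the end of follow-up. The risk ratio (RR) is the share with an AE among positives divided by the share among evaluable negatives. The true value is 1.

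| Setting | Spurious RR |
|---|---|
| Constant onset, AEs do not stop treatment, 20% dropout | about 1.08–1.12 |
| Same, 40% dropout | about 1.16–1.24 |
| Constant onset, half of AEs stop treatment and sampling | about 0.80–0.97 |
| Constant onset, all AEs stop treatment and sampling | about 0.50–0.68 |
| Same, with a 3-month follow-up sample for all | about 0.57–0.76 |
| Early onset, AEs do not stop treatment | about 1.01–1.05 |

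When AEs do not stop treatment, about 53–60% of the AEs in positive subjects precede the first positive sample under constant onset. Under early onset the share is about 24–31%.

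**Why it happens: two single runs** (ADA and AE rates set by 18 months)
1. 40% dropout by 12 months, 40% ADA, 20% AE risk, AEs not stopping treatment. Mean time on drug is 16.03 months in positives and 13.23 in negatives, a ratio of 1.21. AE shares are 17.9% and 14.9%, so RR = 0.179/0.149 = 1.20. Nearly all of the spurious excess is time on drug.
2. 20% dropout by 12 months, 40% ADA, 20% AE risk, every AE stopping treatment. AE shares are 9.4% and 17.5%, so RR = 0.094/0.175 = 0.54. Time on drug is 16.55 and 14.25 months, a ratio of 1.16. Dividing by exposure gives 0.537/1.161 = 0.46, which is further from 1. Exposure adjustment of the fixed split is therefore not enough by itself.

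**Check of the remedy.** With ADA as a time-updated status stratified by time on study, run 1 gives 1.00 and run 2 gives 1.00. Across runs with 20–40% ADA and 10–50% AE risk by 18 months, the null rate ratio is 0.99–1.01 when AEs do not stop treatment. It is 0.94–1.03, within simulation noise, when they do.

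**The case against.** The strongest reply is that the SAP does not commit to a crude comparison. It gives no effect measure, counting rule or time order for the ADA-AE analysis. It restricts attention to AEs attributable to immunogenicity without saying how timing enters that judgement, and it refers to a separate ADA plan that may supply the method. This stands in part. A reader might infer that the SAP orders AEs before ADA onset to be counted against positives, but it says no such thing. What the SAP does fix is the grouping, and it describes the separate plan as holding more analyses. Nothing in the SAP prevents a plain two-group table.

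A reader might also infer that the bias is inevitable. It is not. Its size and sign depend on when ADA arises and whether AEs end treatment, and the SAP gives neither. With early onset it almost vanishes.

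A reader who counts subjects with no post-dose sample as negative would find larger figures: 1.15–1.23 at 20% dropout, 1.34–1.49 at 40%, and 0.42–0.62 if every AE stops treatment. The evaluable rule excludes those subjects. They are not few: 1 − 0.8^0.25 = 5.4% or 1 − 0.6^0.25 = 12.0% would leave before a 3-month sample.

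The SAP also mentions a 3-month follow-up sample. This softens the reversal (0.82–1.01 if half of AEs stop treatment). It does not remove the upward bias, which is 1.09–1.27 when AEs do not stop treatment and those within 3 months after the last dose also count.

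**Conclusion.** The point holds in this form: Section 5.6.4 fixes a post-baseline, ever-positive split for efficacy and safety and states no safeguard against time-on-drug selection or reversed time order. Section 5.3.4 repeats the problem by listing neutralizing ADA beside baseline subgroups.

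Under the stated assumptions the upward bias is modest, roughly 8–24%. The more serious risk is a false reduction if AEs end treatment before ADA is detected, with the risk ratio at about one half to two thirds in the extreme case. All of these figures depend on assumed sampling, seroconversion and AE rates; only dropout and treatment length come from the SAP. They show what a crude comparison could do and do not predict this trial's result.

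The analysis is supportive, with no decision or error control attached, and the primary result is unaffected. Confidence is medium because the separate ADA plan was not available.

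**What to change.** **In Section 5.6.4, for the ADA-AE analysis:**
- Count person-time and AEs as ADA positive only from the first positive post-dose sample (a new response, or a titer raised above the pre-treatment level), and as negative before it. Apply the same rule to neutralizing ADA.
- Report exposure-adjusted AE rates by arm on that basis. A Cox model with time-dependent ADA status is optional.

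**In Sections 5.6.4 and 5.3.4, for efficacy by ADA or neutralizing ADA:** use status at a stated landmark visit, or label the analysis descriptive. A landmark removes the dependence on later follow-up but does not create a matching placebo group, so contrasts with placebo remain non-randomized.

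Align the separate ADA plan with these rules.

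**Cost:** a few lines of SAP text and modest programming on existing sample and AE dates. There will be fewer events in the positive state, so intervals will be wider. The first positive sample marks detection and not onset, so events between the two still count as negative.

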5.6.5 Laboratory Values

Laboratory results will be summarized using Système International (SI) units, as appropriate. For all quantitative parameters listed in [protocol Section 9.5.1.5 Safety Assessments \(Laboratory Measurements\)](#), the actual value and the change from baseline to each post-baseline visit and to the end of treatment (defined as the last on-treatment value) will be summarized by visit and treatment group using descriptive statistics. Qualitative parameters listed in [protocol Section 9.5.1.5](#) will be summarized using frequencies (number and percentage of subjects), and changes from baseline to each post-baseline visit and to end of treatment will be reported using shift tables. Percentages will be based on the number of subjects with both non-missing baseline and relevant post-baseline results.

Laboratory test results will be assigned a low/normal/high (LNH) classification according to whether the value was below (L), within (N), or above (H) the laboratory parameter's reference range. Within treatment comparisons for each laboratory parameter will be based on 3-by-3 shift table that compares the baseline LNH classification to the LNH classification at each post-baseline visit and at the end of treatment. Similar shift tables will be used to compare the baseline LNH classification to the LNH classification for the highest and lowest value during the treatment period.

The Sponsor's Grading for Laboratory Values (see [Appendix 13.1](#)) presents the criteria that will be used to identify subjects with treatment-emergent markedly abnormal laboratory values (TEMAV). Except for phosphate, a TEMAV is defined as a post-baseline value with an increase from baseline to a grade of 2 or higher. For phosphate, a TEMAV is defined as a post-baseline value with an increase from baseline to a grade of 3 or higher. When displaying the incidence of TEMAVs, each subject will be counted once in the laboratory parameter high and in the laboratory parameter low categories, as applicable.

5.6.6 Vital Signs

Descriptive statistics for vital signs parameters (diastolic and systolic blood pressure, pulse, respiration rate, temperature and weight) and changes from baseline will be presented by visit and treatment group.

In addition, frequency counts of clinically notable vital signs will be summarized by treatment group. Table 3 presents the clinical notable ranges.

Table 3: Clinical Notable Ranges for Vital Signs

Vital Sign	Criterion for Low	Criterion for High
Pulse (bpm)	< 50	> 100
Temperature (°C)	< 36	> 38
Weight (kg)	< 45	> 100
Systolic BP	< 90	> 160
Diastolic BP	< 50	> 100

5.6.7 Electrocardiograms

Abnormal ECG findings will be presented as shifts from baseline (normal/abnormal clinically significant/abnormal not clinically significant) to post baseline (normal/abnormal clinically significant/abnormal not clinically significant) visits. The number and percent of subjects will be presented.

5.6.8 Other Safety Analyses

No other safety analyses are planned for this study.

5.7 OTHER ANALYSES

Other analyses may be conducted as ad-hoc to investigate impact of intercurrent events (e.g., early discontinuation and initiation of new AChEIs or memantine) on study outcomes. The reason and timing of intercurrent events, data collected after intercurrent events, missing data

mechanisms and different statistical methods for handling missing data may be explored as appropriate. Impact of potential correlation or interaction between baseline status and disease course and between subject subgroups and treatment groups on the study outcomes may be explored as appropriate. Any ad-hoc analyses that are performed will be appropriately titled/labeled as ad-hoc and will be clearly distinguished from planned analyses if results are reported in the Clinical Study Report.

